8.2.2 Secondary endpoints

For secondary endpoints, due to the small sample size in this pilot study, descriptive statistics with mean and 95% confidence intervals will be used. For continuous variables, descriptive statistics will include the number of non-missing values, mean, standard deviation, median, min and maximum. For categorical variables, descriptive statistics will include counts and percentages per category. For comparison between subgroups, ANOVA and t-tests will be used when appropriate to determine the association of the efficacy endpoints and specific biomarkers.

8.2.2.1 Safety and tolerability

Safety events will be classified using NCI CTCAE v.4.03 (https://ctep.cancer.gov/).

Overall rates of AE and SAE will be summarized based on frequency and proportion of total subjects, by system organ class, preferred term, Grade, and investigator-assessed relationship to sorafenib, nivolumab, or the combination. Dose reductions, dose delays, and discontinuations for toxicity will be summarized.

8.2.2.2 Rate of irAE for combination overall and in Child Pugh B patients

Safety events assessed by treating investigator and/or Study Chair as being at least possibly Immune-related on nivolumab (irAE) will be summarized based on frequency and proportion of total subjects, by system organ class and preferred term as for overall safety. Rate of irAE in Child Pugh B patients in Part 2 will also be summarized.

8.2.2.3 ORR by RECIST 1.1 for overall study and in Parts 1 and 2 individually

ORR is a key secondary endpoint and will be based on RECIST 1.1⁵ as assessed by local radiographic review. ORR will be analyzed for all efficacy-evaluable patients (Parts 1 and 2 combined) as well as for Part 1 and Part 2 individually. ORR defined as the proportion of subjects with RECIST 1.1-measurable disease at study entry (which is required for eligibility) who have a CR or partial response (PR) using RECIST 1.1 at any time during the main study. Subjects with measurable disease at study entry who have unknown or missing response information will be treated as non-responders.

The ORR of sorafenib was approximately 2% in SHARP trial,² and the ORR of nivolumab as monotherapy was 10.2% in Child Pugh B7-8 patients treated with nivolumab in the Child Pugh B cohort of CheckMate 040.³ The ORR of nivolumab in Child Pugh A patients treated with nivolumab as 1st line therapy in CheckMate 459 was 15%.⁴ Thus, an ORR of at least 15% for the combination of sorafenib plus nivolumab in this study would be an encouraging signal of efficacy, if accompanied by acceptable safety in Child Pugh B patients in Part 2 as defined above, and would warrant consideration of a larger study.

For the overall study population, a sample size of 24 evaluable patients from Parts 1 and 2 combined T will have 83% power with 1-sided alpha of 5% to determine true ORR >15%, using Chi-square tests with 1-sided alpha of 5%.

8.2.2.4 Duration of response (DOR), PFS, and OS for Child Pugh B Expansion Cohort and overall study population

In subjects who achieve PR or CR, DOR is defined as the time from first documented evidence of CR or PR until the first documented sign of disease progression or death. For all patients, PFS will be calculated in months from date of first dose of protocol therapy to date of first documented radiographic and/or clinical disease progression or

death from any cause. For patients discontinued from study for other reasons than progression or death (see Section 5.2), PFS will be censored at the date last known to be progression-free. OS is defined as the time from the date of first dose of protocol therapy to the date of death due to any cause. Censoring will be performed using the date of last known contact for those who are alive at the time of analysis.

Median DOR, median PFS and OS will be summarized overall and according to treatment group. Kaplan-Meier medians and quartiles may be provided if data warrant. If data warrant, Kaplan-Meier quartile estimates along with the 95% CI will be calculated. Descriptive summaries including swim lane plots may also be generated depending on results.

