1.2 Rationale of the study

The multikinase inhibitor sorafenib, whose principal targets include VEGFR2, VEGFR3, and RAF kinases, is the only approved first-line therapy with established survival benefit in patients with HCC not amenable to curative therapies.^{1,2} Though the survival benefit of sorafenib has been consistent across multiple studies, the overall magnitude of benefit is small, and generally fewer than 5% of patients demonstrate response by conventional Response Evaluation Criteria in Solid Tumors (RECIST) across studies.¹⁻³

Recently, the anti-programmed death-1 receptor (PD-1) inhibitor, nivolumab, demonstrated a preliminary signal of efficacy in the CheckMate 040 Phase I/II trial in advanced HCC patients, including a dose escalation cohort of 48 patients and a dose expansion cohort of 214 additional patients, across etiologic subtypes.⁴ In the dose expansion cohort, tumor responses occurred in 20%, median duration of response has not yet been reached but was over 17 months for the dose escalation cohort. Results of CheckMate 040 have led to an ongoing multinational Phase III trial, CheckMate 459 [NCT02576509] comparing the efficacy of sorafenib versus nivolumab as first-line therapy for advanced HCC.

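### The 83% power for ORR in Section 8.2.2.3 has no stated null and alternative, and no pair of the response rates in that section reproduces it

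*Combined protocol and SAP*

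**What the plan says.** Section 8.2.2.3 calls ORR a key secondary endpoint and cites three reference rates:

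- sorafenib: "The ORR of sorafenib was approximately 2% in SHARP trial"
- nivolumab in Child Pugh B7-8 patients (CheckMate 040): 10.2%
- first-line nivolumab in Child Pugh A patients (CheckMate 459): 15%

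It treats an ORR of at least 15% as encouraging, "if accompanied by acceptable safety in Child Pugh B patients in Part 2 as defined above, and would warrant consideration of a larger study". The next paragraph takes "a sample size of 24 evaluable patients from Parts 1 and 2 combined" and says that this number "will have 83% power with 1-sided alpha of 5% to determine true ORR >15%, using Chi-square tests with 1-sided alpha of 5"%. No null rate and no alternative rate is named.

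Section 8.2.2 says that for secondary endpoints "descriptive statistics with mean and 95% confidence intervals will be used". Section 8.4 gives a total sample size of 6-24, so 24 is the maximum.

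**The concern.** Power for a one-sample test of a proportion is defined only once a null rate and an alternative rate are fixed. The phrase "to determine true ORR >15"% reads most naturally as a test of the null that ORR is 15% or less, but then the alternative is missing. If 15% is meant as the alternative, the null is missing, and rejecting a much lower null would not show that the true ORR exceeds 15%.

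A reader therefore cannot reproduce the 83% or tell what a significant result would mean. On the literal reading, the study has far less power than the sentence suggests unless the true ORR is in the mid-30s or higher. A chi-square approximation is also a doubtful choice with so few expected responders, and the plan does not say whether a continuity correction applies.

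**Working it through.** **Inputs (Section 8.2.2.3).** n = 24 in a single group; one-sided alpha 5%, so z = 1.645; candidate rates 2%, 10.2% and 15%; stated power 83%.

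**Formulas.** For null p0 and alternative p1:

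- Uncorrected approximation: power = Φ{[p1 − p0 − 1.645·√(p0(1−p0)/24)] / √(p1(1−p1)/24)}.
- Continuity-corrected: subtract a further 0.5/24 = 0.0208 inside the square bracket.
- Exact: find the smallest r with P(X ≥ r | 24, p0) ≤ 0.05; power is P(X ≥ r | 24, p1).

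**Attempt to reproduce 83%, using 2% against 15%.** The standard errors are √(0.02×0.98/24) = 0.0286 and √(0.15×0.85/24) = 0.0729.

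- Uncorrected: (0.13 − 0.0470)/0.0729 = 1.139, power 87.3%.
- Corrected: (0.13 − 0.0208 − 0.0470)/0.0729 = 0.853, power 80.3%.
- Exact: reject at ≥3/24, alpha 1.2%, power 72.0%.

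**All three pairs of the section's rates:**

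| Null vs alternative | Uncorrected | Corrected | Exact |
|---|---|---|---|
| 2% vs 15% | 87.3% | 80.3% | 72.0% |
| 2% vs 10.2% | 71.4% | 59.1% | 44.9% |
| 10.2% vs 15% | 23.1% | 15% | 13.9% |

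None gives 83%.

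**Literal reading, null ORR ≤15%.** Solving for 83% power gives p1 = 36.4% by the uncorrected approximation: (0.214 − 0.1199)/0.0982 = 0.958, Φ = 0.83. By the exact test p1 is about 41%. Power at other true rates is:

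| True ORR | Exact test (reject at ≥8/24 = 33.3%, alpha 2.0%) | Chi-square test (reject at ≥7/24 = 29.2%, true alpha 5.7%) |
|---|---|---|
| 30% | 44% | 61% |
| 35% | 64% | 79% |
| 40% | 81% | 90% |

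**If 15% is the alternative to 2%.** The test rejects at 2/24 (8.3%) uncorrected, or at 3/24 (12.5%) corrected or exact. Both observed rates lie below 15%, so rejection cannot support a claim that the true ORR exceeds 15%.

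**Behaviour of the chi-square test.** Expected responders under the null are 24×0.02 = 0.48, 24×0.102 = 2.45 and 24×0.15 = 3.60. Binomial type I error of the z ≥ 1.645 rule:

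| Null | Uncorrected: cut-off, true alpha | Corrected: cut-off, true alpha |
|---|---|---|
| 2% | ≥2, 8.3% | ≥3, 1.2% |
| 10.2% | ≥5, 9.1% | ≥6, 3.0% |
| 15% | ≥7, 5.7% | ≥7, 5.7% |

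**A possible origin.** A null of 5% against 20% gives (0.15 − 0.0732)/0.0816 = 0.941, power 82.7% uncorrected, which rounds to 83% (73.6% exact). Section 1.2 says of sorafenib that "generally fewer than 5% of patients demonstrate response" and of nivolumab "In the dose expansion cohort, tumor responses occurred in 20"%. The power sentence cites neither rate, and neither matches its 15%. That the figure survives from hypotheses no longer stated is an inference.

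**The case against.** The strongest reply is that this is an omission and not an arithmetic error. Without a stated pair, 83% cannot be shown to be miscalculated. For 2% against 15% the answer depends on the method: 72.0% exact, 80.3% corrected, 87.3% uncorrected, and 89.4% for the true power of the uncorrected chi-square rule. These values lie on both sides of 83%. The 2% is itself approximate, and 5% against 20% does give the stated figure.

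The first part stands: the finding is that the power is unspecified and cannot be reproduced, not that a known calculation went wrong. The rest does not rescue the sentence. A null of 2.5% still gives 84.0% uncorrected, and a two-sided 5% test of 2% against 15% gives 84.5% but contradicts the one-sided alpha stated twice. If 5% and 20% were the hypotheses, the plan needs to say so and drop the reference to 15%.

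The second reply is that little depends on this. ORR is secondary in a pilot study; the sample size in Section 8.4 is not derived from it; the criterion for a larger study is an ORR of at least 15% with acceptable safety, not this test; and the version is dated 03/09/2022, with accrual due to close by 30 April 2022. All of that stands and limits the consequence. It does not justify keeping an uncheckable power claim for an endpoint the plan calls key, particularly when Section 8.2.2 already provides for a descriptive analysis.

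**Conclusion.** The concern holds. The sentence lacks a null/alternative pair, and no pair of the rates cited in Section 8.2.2.3 gives 83% at n=24 and one-sided 5%; the nearest, 2% against 15%, gives 87.3%, 80.3% or 72.0% depending on method. For the claim as worded, 83% power would need a true ORR of about 36% to 41%, which the plan does not state. At a true ORR of 30%, power is 44% exact, or 61% for the chi-square rule.

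These figures assume a one-sample test and all 24 patients evaluable. The sentence should be corrected, but the primary endpoints and the sample size do not depend on it.

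**What to change.** **Preferred.** Delete the power and chi-square sentence and, in line with Section 8.2.2, write for example: *ORR will be reported with an exact (Clopper-Pearson) 95% CI. With 24 evaluable patients, the planned maximum, 4 responses (16.7%) give 4.7% to 37.4% and 8 responses (33.3%) give 15.6% to 55.3%.* Eight is the smallest count whose interval excludes 15%; 7/24 gives 12.6% to 51.1%.

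**If a test is kept.** State the null, the alternative and an exact binomial rule with its true alpha and power. Two options:

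- Null ORR ≤15%: reject at ≥8/24, alpha 2.0%, power 44% at a true ORR of 30% and 81% at 40%.
- Null ORR ≤2%: reject at ≥3/24, alpha 1.2%, power 72% at 15%. This must not be described as a test that ORR exceeds 15%.

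**Cost.** One sentence of wording and no extra patients. The stated power either disappears or becomes less favourable.

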8.2.3 Exploratory endpoints

For exploratory endpoints, due to the small sample size in the study, descriptive statistics with mean and 95% confidence intervals will be used. Depending on funding availability, we plan to explore immunologic and genomic biomarkers (including PBMC T cell subsets and TCR frequency and diversity, tumor immune subset composition and immune infiltrates) for relationships to clinical features including etiology of liver disease, baseline liver function, and to the primary and secondary efficacy endpoints. No type I error will be adjusted for multiple endpoints. For continuous variables, descriptive statistics will include the number of non-missing values, mean, standard deviation, median, min and maximum. For categorical variables, descriptive statistics will include counts and percentages per category. For comparison between subgroups, ANOVA and t-tests will be used when appropriate to determine the association of the efficacy endpoints and the specific biomarkers. For association between biomarkers, Spearman correlations will be calculated to determine the significance of the association between the biomarkers of interest. A selection of planned analyses is described further below.

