5.1 Eligibility

5.1.1 Inclusion criteria

- Histologic or cytologic diagnosis of unresectable, locally advanced and/or metastatic HCC not amenable to curative surgery, transplantation, or ablative therapies based upon assessment of treating investigator
 - For patients without prior histologic or cytologic diagnosis, radiographic diagnosis is allowed provided patients meet American Association for the Study of Liver Diseases (AASLD) criteria for radiographic diagnosis 44
- 2. Radiographically measurable disease by RECIST version 1.1 in at least one site not previously treated with chemoembolization, radioembolization, radiation, or other local/liver-directed procedures (i.e. must have at least one measurable target lesion, either within the liver or in a measurable metastatic site); a new area of tumor progression within or adjacent to a previously-treated lesion, if clearly measurable by a radiologist, is acceptable
- 3. Untreated/pretreatment archival tumor tissue must be available for correlative analyses
- 4. Age at least 18 years at enrollment
- 5. ECOG 0 or 1 at enrollment
- At least 4 weeks after any prior chemoembolization, radioembolization, local ablative therapies, or hepatic radiation and recovery to ≤ grade 1 treatmentrelated toxicity
- 7. At least 6 weeks after any major surgery including prior hepatic resection and recovery to ≤ grade 1 treatment-related toxicity
- 8. At least 7 days after minor surgery (such as central venous access) or biopsy and recovery to ≤ grade 1 treatment-related toxicity
- 9. At least 2 weeks after any prior palliative radiation (e.g. to focal metastatic lesion such as bone metastases) and recovery to ≤ grade 1 treatment-related toxicity
- 10. Blood pressure ≤140/90 mm Hg with or without anti-hypertensive therapy
 - a. Patients may be rescreened after initial ineligibility if due to elevated blood pressure, if adequately medically managed within approximately 30 days
- 11. Adequate baseline organ and marrow function as defined below:
 - a. adequate bone marrow function:
 - absolute neutrophil count at least 1,200/mcL platelets at least 50,000/mcL hemoglobin at least 9 g/dL
 - b. adequate hepatic function:
 - Part 1: total bilirubin less than 2.6 mg/dL or 2 times ULN, whichever is higher, and albumin at least 2.5 g/dL if otherwise meets criteria for Child Pugh A or B7

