- Part 2: total bilirubin less than 3.9 mg/dL or 3 times ULN⁴¹, whichever is higher, and albumin at least 2.0 g/dL, if otherwise meets criteria for Child Pugh B
- Part 1: AST(SGOT) and ALT (SGPT) less than 5 X ULN, INR less than 1.7 Part 2: AST(SGOT) and ALT (SGPT) less than 8 X ULN, INR less than 1.7
- c. creatinine less than 1. 5 X ULN and/or creatinine clearance ≥ 60 mL/min
- 12. Child Pugh A or B7 (Part 1); Child Pugh B7-9 (Part 2) (See Appendix 14.3)
- 13. If HBV sAg and/or core Ab positive, must be treated with appropriate antiviral therapy according to institutional practice with HBV DNA by PCR less than 500 IU/mL
- 14. If clinical or histologic diagnosis of cirrhosis and/or clinical or radiographic evidence esophageal or gastric varices, must have had EGD surveillance and adequate endoscopic therapy according to institutional standards
- 15. Able to swallow and retain oral medications
- 16. Women of child-bearing potential (WOCBP) must have a negative pregnancy test within 28 days before study enrollment
- 17. WOCBP and male partners of WOCBP must agree to use two methods of contraception until at least 5 months after last dose of each study drug for WOCBP subjects, and 7 months for male partners of WOCBP
- 18. Able to understand and willingness to provide informed consent, and the willingness to comply with the requirements of the protocol
 - a. Subjects must have signed and dated an IRB/IEC approved written informed consent form in accordance with regulatory and institutional guidelines and before the performance of any protocol related procedures that are not part of standard of care

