6.1 Treatments to be administered

All patients will be treated with the combination of sorafenib plus nivolumab. Patients will be enrolled to one of two sequential cohorts: the Dose Escalation Cohort (Part 1) or the Child Pugh B Expansion Cohort (Part 2). Patients enrolled to the Dose Escalation Cohort (Part 1) will be enrolled starting at Dose Level -1 according to Table 6.2.1-1 below, following standard 3+3 dose escalation rules as outlined in Section 6.2.2 below. Patients enrolled to the Child Pugh B Expansion Cohort (Part 2) will be enrolled to the maximum tolerated dose (MTD) of sorafenib identified in Part 1 along with standard dose nivolumab, as described below in Section 6.2.2.

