8.2.3.1 PBMC immune cell subset frequencies and relationship to treatment and clinical outcomes

Serial blood samples for PBMC analyses will be collected at time points in Section 7.1, Schedule of procedures. Immune cell subsets will be measured using flow cytometry as has been previously described, or similar updated methods.^{29,30} PBMC analyses for all patients will be performed in the UCSF CIL.

Baseline levels of individual PBMC T cell and other immune cell subset components as well as change in levels on combination treatment will be explored for relationship with ORR, baseline liver function, as well as secondary efficacy endpoints (including PFS, DOR, OS) to determine if there is an association using Fisher's Exact tests.

8.2.3.2 PBMC T cell receptor (TCR) clonotype frequency and diversity and relationship to treatment and clinical outcomes

If funds are available, the frequency of individual TCR clonotypes and the diversity of overall TCR clonotype repertoire from PBMC samples will be measured by next-generation sequencing as has been previously described or by a similar, updated methodology.³¹ PBMC analyses for patients enrolled at UCSF will be performed in UCSF CIL.

The frequency of TCR clonotypes with identical sequences³¹ will be calculated by dividing the number of identical sequence reads by the total number of sequencing reads for that sample. TCR repertoire diversity will be calculated as the number of unique clonotypes comprising the top 25% of cumulative reads sorted by abundance.³¹ Baseline frequency and diversity as well as changes on combination treatment will be explored for relationship with ORR, baseline liver function, as well as secondary efficacy endpoints using Fisher's Exact tests.

PBMC TCR clonotype diversity/frequency will also be described at baseline and after starting combination therapy in Part 2 to characterize the time course of these effects and to better understand the relative impact of each study drug.

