8.4 Determination of sample size

The total sample size will be 6-24 patients for Parts 1 and 2 combined.

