APPENDIX 3: Child Pugh score

The Child Pugh score will be calculated using the modified Child Pugh scoring system⁴⁶ at time points specified in Section 7.1, Schedule of procedures. Ascites should be assessed by clinical examination (rather than radiographic findings). Encephalopathy and ascites are considered as present (i.e. at least 2 points) in any patient taking medications for these conditions (e.g., lactulose, diuretics) even if well-controlled at the time of Child Pugh score assessment.

		Points assigned	
Parameter	1	2	3
Ascites	none	mild/moderate (diuretic-responsive)	tense (diuretic- refractory)
Total bilirubin, mg/dL	< 2	2-3	> 3
Albumin, g/dL	> 3.5	2.8-3.5	< 2.8
Prothrombin time		± ±	
Seconds over control	1–3	4–6	> 6
or			
INR	< 1.7	1.7-2.3	> 2.3
Encephalopathy	none	Grade 1-2 (or precipitant-induced)	Grade 3-4 (chronic)

Child-Pugh score (A, B, or C) based on total score from the above point assignments:

Grade	Points	1-year survival	2-year survival
A: well-compensated disease	5–6	100%	85%
B: significant functional compromise	7–9	80%	60%
C: decompensated disease	10-15	45%	35%

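### Pooled biomarker associations with PFS and OS span Child Pugh A to B9 unadjusted, so a marker that tracks liver function can give a biased result

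*Combined protocol and SAP*

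**What the plan says.** Section 6.1 sets up the cohorts: "Patients will be enrolled to one of two sequential cohorts". Section 5.1.1 selects them on different liver function, "Child Pugh A or B7 (Part 1); Child Pugh B7-9 (Part 2"), and sets different laboratory limits. For bilirubin these are "Part 1: total bilirubin less than 2.6 mg/dL or 2 times ULN" against "Part 2: total bilirubin less than 3.9 mg/dL or 3 times ULN", in each case whichever is higher. Albumin and AST/ALT limits are also looser in Part 2.

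Section 2.3 states the exploratory objectives for Parts 1 and 2 together. Its first two list immune marker, baseline liver function and clinical outcome in one line. Section 8.2.3 then relates the markers "for relationships to clinical features including etiology of liver disease, baseline liver function, and to the primary and secondary efficacy endpoints". For PBMC subsets, Section 8.2.3.1 relates the marker to ORR and baseline liver function "as well as secondary efficacy endpoints (including PFS, DOR, OS) to determine if there is an association using Fisher's Exact tests". Sections 8.2.3.2 and 8.2.3.3 name Fisher's exact test in the same way for TCR measures and tumor infiltrates, and Section 8.2.3 adds ANOVA and t-tests. None of these sections makes Child Pugh class, Child Pugh score or Part a stratum or covariate in a marker-outcome test. For ORR itself, Section 8.2.2.3 does report each Part separately.

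**The concern.** Liver function can be linked both to the marker and to survival. Appendix 3 gives 1-year and 2-year survival of 100% and 85% for class A, and of 80% and 60% for the class it describes as "B: significant functional compromise". Combining patients across these classes and testing marker against outcome without adjustment leaves liver function as a possible confounder.

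The plan would show whether a marker goes with liver function and, separately, whether it goes with survival. It would not show whether the marker is informative among patients of similar liver function, which is the question raised by listing the three together in Section 2.3. At stake is which markers are carried forward as candidates. In a descriptive analysis the biased estimate matters at least as much as the p-value.

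**Working it through.** The plan gives no power or error rate for these analyses, so there is no figure of its own to reproduce. The check takes a marker with no effect within class and asks what the pooled analysis shows.

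**Inputs from the documents.** Two-year survival 85% (A) and 60% (B), Appendix 3. Median OS 15.0 months in the nivolumab dose-escalation cohort, Section 1.4.2. ORR 15% (Child Pugh A) and 10.2% (B7-8) on nivolumab, Section 8.2.2.3. Sample size, Section 8.4: "The total sample size will be 6-24 patients for Parts 1 and 2 combined", with 6-12 in Part 1 and 12 in Part 2.

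**Assumptions.** Two-sided 5% level (none is stated). Class split 12 A/12 B, the most class A patients possible, or 6/18 if half of Part 1 is B7. The strength of the marker's link to class is not given and is shown as a range.

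**1. Bias in the estimate.** Take a binary marker present in 90% of class A and 10% of class B, 12 patients per class.
- Marker-positive: 10.8 A + 1.2 B. Expected 2-year survivors: 10.8 × 0.85 + 1.2 × 0.60 = 9.9 of 12.
- Marker-negative: 1.2 A + 10.8 B. Expected survivors: 1.2 × 0.85 + 10.8 × 0.60 = 7.5 of 12.
- Pooled odds ratio: (9.9/2.1) / (7.5/4.5) = 2.83. Within class it is 1.0 by construction.

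The same arithmetic gives 1.29, 1.66 and 2.15 for prevalences of 60/40, 70/30 and 80/20.

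**2. False positives, Fisher's exact test on 2-year survival (12/12).** Using Fisher's test for OS requires reducing it to status at a fixed time; 2 years is assumed here.

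| Prevalence A/B (%) | Pooled Fisher | Stratified (Mantel-Haenszel) |
|---|---|---|
| 60/40 | 3.0% | not run |
| 70/30 | 4.3% | 4.8% |
| 80/20 | 7.3% | 4.1% |
| 90/10 | 11.7% | 3.4% |
| 100/0 | 14.3% | never rejects |

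With no link to class, Fisher rejects in 2.7%. At 6/18 it stays at or below 5.0%.

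**3. False positives, t-test on a continuous marker by 2-year survival (12/12).** For shifts of 0.5, 1, 2 and 3 SD: 5.7%, 8.8%, 16.1% and 21.2% pooled, and 4.6-5.0% with class as covariate. At 6/18 the pooled rate is at most 10.6%.

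**4. False positives, median-split log-rank test.** The plan does not name this test, but it is the natural one for PFS and OS. Follow-up is 24 months and the marker is shifted 1 SD between classes.
- *Mixed inputs.* Hazard ratio = ln 0.60 / ln 0.85 = 3.14, applied to a 15-month class-A median. Result: about 15% unstratified and about 6% stratified. Shifts of 0.5 and 2 SD give about 8% and 37% unstratified. With a hazard ratio of 2.0, 1 SD gives 9-10% against about 6%. At 6/18 and hazard ratio 3.14 it is about 11% against 7%.
- *Appendix 3 survival in both classes.* About 7% unstratified and about 5% stratified. At 6/18, about 6% against 5.4%.

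The two versions differ because the first implies far more deaths than Appendix 3. Class-A 2-year survival would be 0.5^(24/15) = 33%, and class B 0.33^3.14 = 3%, with a class-B median of 15/3.14 = 4.8 months.

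**5. ORR.** With 15% against 10.2%, the pooled odds ratio is at most (0.15/0.85)/(0.102/0.898) = 1.55. Fisher rejects in about 1% and the t-test in 4-5%, so there is practically no inflation.

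**The case against.** The analyses are exploratory, descriptive and dependent on funding, and Section 8.2.3 disclaims type I error adjustment, so the plan does not promise the error rate measured above. That stands, and it limits the seriousness of the point; it does not remove the bias in the estimates.

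Liver function is also examined from each side. Markers are related to it, and a further objective in Section 2.3 relates clinical outcomes to baseline liver function. A careful reader of all three results could suspect confounding. That stands too, but three pairwise comparisons do not give the adjusted association.

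Pooling is not stated in so many words, and Section 8.2.3 calls what follows a selection of planned analyses, so a within-class analysis is not ruled out. Reading the objectives for Parts 1 and 2 as pooled is natural but remains an inference. Nor are the Parts a clean A-versus-B contrast: they overlap at B7, and PBMC are collected at one site only.

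A reader might infer that any marker varying with liver function will appear prognostic. The documents do not support that. Even with the harsher inputs, a null marker shifted 1 SD reaches significance in about 15% of trials, so most such markers would not. Fisher's test, the one the plan names, exceeds 5% only when marker and class are strongly linked.

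**Conclusion.** The point holds as a modest one. Across Child Pugh A to B9, the named marker-outcome tests are unadjusted, so a marker that tracks liver function can show a biased pooled association with PFS or OS. The plan cannot tell that apart from information beyond liver function.

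For a null marker the pooled 2-year survival odds ratio is 1.29 to 2.83 over the prevalences examined. At a 1 SD shift and a 12/12 split, the log-rank false-positive rate is about 7% to 15%, against about 5-6% when stratified. The lower figure uses Appendix 3 survival throughout. The upper one combines its hazard ratio with a median from another source and should be read as a sensitivity case. Appendix 3 is a general Child Pugh table, and a wider survival gap in this population would raise the rates. PFS was not simulated; the argument extends to it only if PFS also differs by class. For ORR the effect is negligible. No decision rule in the plan depends on these analyses, so this is a worthwhile refinement and not a flaw in the trial's main conclusions.

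**What to change.** In Section 8.2.3, for every pooled marker-PFS and marker-OS association, add an analysis stratified by baseline Child Pugh class (stratified log-rank test or stratified Cox model). Present it beside the pooled result and label the pooled result unadjusted. For ORR, tabulate responders by marker within Child Pugh class, without a test. At 15% of 24 there would be about 3.6 responders, too few for a stratified exact test to be useful.

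The cost is SAP wording only, since the Child Pugh score is already recorded at screening. Strata of about 6 to 18 patients, fewer for PBMC markers, will lose some power. Class strata leave differences between B7 and B9 unadjusted. A marker that coincides fully with class cannot be separated from it by any analysis, and the report should say so if that occurs.
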